3.3 Definition of dose limiting toxicity

Therapeutic IgGs such as trastuzumab, alemtuzumab or rituximab, and related proteins commonly cause infusion-related reactions. These reactions are thought to be due to cytokine release and typically are most frequent and severe with the first infusion, declining in incidence and severity thereafter. Such reactions are generally managed by slowing or interrupting the infusion. It is possible that MOv18 IgE will cause these non-specific infusion-related reactions, which are biologically distinct from anaphylaxis, although it can be difficult to distinguish them clinically.

Despite pre-clinical evidence suggesting otherwise, it is possible that MOv18 IgE may also cause anaphylaxis due to basophil and/or mast cell degranulation. Such a reaction would be predicted to persist and probably worsen with subsequent infusions. Slowing or interrupting the infusion would typically be insufficient to control such a reaction and systemic therapy, including administration of adrenaline, might be needed.

Clinically, the symptoms, signs and onset of typical cytokine release-type infusion reactions are very similar to those associated with IgE-mediated basophil and/or mast cell degranulation/anaphylaxis and it may be difficult to distinguish these different types of acute reaction in a patient receiving their first dose. However, the presence of urticaria is almost universal in reactions due to mast cell degranulation, but is not typical of infusion reactions seen with protein-based therapeutics such as IgGs (although it can occur). Importantly, emerging data from the CRUKD14001 study indicate that urticaria without systemic symptoms is common with MOv18 IgE and does not necessarily indicate the onset of anaphylaxis. Serum tryptase elevation (a marker of mast cell degranulation) would not be expected to occur with cytokine release-type infusion reactions (Cheifetz *et al.*, 2003), and for this study is considered critical in distinguishing these two types of reactions clinically.

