If the patient experiences symptoms suggestive of an infusion-related reaction or cytokine release (such as fever, chills, and myalgia), the infusion must be slowed or interrupted and the patient must be treated with oxygen, paracetamol, antihistamines, fluid resuscitation and/or steroids, as clinically indicated. If the reaction does not respond to these conservative measures or is > Grade 2 in severity, the algorithm for the treatment of anaphylaxis must be followed (Appendix 4). Note that for the purposes of this protocol, infusion-related symptoms and signs (such as fever, myalgia, and hypotension) will be recorded and graded individually according to NCI-CTCAE Version 4.02. Grading of systemic mast cell degranulation (anaphylaxis) is defined in Appendix 5 and grading of cytokine release syndrome is defined in Appendix 6, but the distinction between these two events and grading of these events will be performed only in retrospect when results of serum tryptase assays are available, and will thus not be relevant for the management of acute events at the time of infusion. A blood test for measurement of serum tryptase will be taken on completion of all infusions. Additional blood samples for serum tryptase levels should be taken in patients who experience a suspected anaphylactic reaction, such as urticaria and/or severe infusion-related symptoms necessitating interruption or discontinuation of the infusion. Additional samples for serum tryptase should also be taken for patients with a positive skin prick test (see study lab manual and protocol section 7.2 for time points). For details on grading and reporting of infusion-related events and anaphylaxis see Section 7.2.5.

The following medications must be available at the bedside for use in case of an immune-mediated reaction: epinephrine (0.5-1mL IM injection 1:1000), chlorphenamine 10 mg IV/IM injection, paracetamol 1 g orally, hydrocortisone 200 mg IM or IV; oxygen (see 16.4 Appendix 4: Treatment of Anaphylaxis).

For patients who are enrolled in an intra-patient escalation cohort, and receive a higher dose in Cycle 2, the following additional measures will apply:

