For Cohorts 5-10 (flat dosing) (1.5 - 50 mg doses of MOv18 IgE), three patients will be enrolled per cohort, with an additional three patients added to a cohort if needed for toxicity, as outlined below (Table 2). No further dose escalation is planned after Cohort 10 (i.e. 50 mg will be the top dose evaluated). For Cohorts 7-9 (intra-patient escalation), a minimum of 1 patient will be enrolled per cohort (see 5.4.1).

If drug supply permits, one or more cohorts may be expanded up to six patients to further explore the safety and efficacy of MOv18 IgE.

One or more cohorts may be repeated but with administration of prophylactic medication (antihistamine, antipyretic and/or corticosteroid), if considered medically appropriate by the Trial Steering Group (see Section 3.6). Under these circumstances, the prophylactic medication should be given after the skin prick test (before IV administration of MOv18 IgE). Any prophylactic medication will be used within its marketing authorisation.

Before commencement of a new cohort, all patients treated at the previous dose level must have received at least three doses and completed at least three weeks since the first dose. For the second patient in any cohort, the first patient in that cohort must have received at least two doses and been followed for at least 24 hours after the last dose. The second, third and subsequent patients in a cohort (if needed) must not receive their first treatments on the same day. If a patient is withdrawn from the study prior to receiving three doses of study medication without experiencing a DLT or a positive skin prick test, a replacement patient will be added to that dose level.

Decisions on dose escalation will be based primarily on toxicities encountered after the first two doses of MOv18 IgE in each cohort (see Table 2), or the first two doses of cycle 2 for patients undergoing intra-patient dose escalation. However, if available, data on toxicities occurring after later doses will also be taken into consideration. The decision to start a new cohort, and selection of the MOv18 IgE dose for each cohort, will be agreed by investigators and sponsor on review of the toxicities experienced by the preceding cohort during the three-week period from first dosing of each patient. The availability of paired pre-treatment and on-treatment tumour biopsies will also be taken into consideration in decisions on starting a new cohort since paired tumour biopsies are required for all patients.

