5.4.1 Intra-patient dose escalations

The established pattern of predictable and tolerable adverse events in Cohorts 1-6 provides reassurance that accelerated dose escalation could proceed subsequently. Intra-patient dose escalation may be initiated from Cohort 7 onwards in order to evaluate alternative doses, depending on emerging safety information and/or pharmacokinetic data if available. An intra-patient dosing schedule has been proposed as per Table 3.

A dose review meeting will be held following completion of Cycle 1 in Cohorts 7 and above, prior to confirming the intra-patient dose escalation for Cycle 2. Should a patient experience any IMP-related AEs of Grade 2* or higher in Cycle 1, then intra-patient dose escalation will not occur, and the patient will continue to be dosed in Cycle 2 based on the flat dose received in Cycle 1 (See Figure 4).

An additional dose review meeting will be held following completion of Cycle 2 prior to confirming the opening of the next cohort. Should a patient experience any IMP-related AEs of Grade 2* or higher in

Cycle 2, then the decision will be made by TSG based on safety data available to either: expand the Cohort by one patient and repeat Cycle 1 and 2 dose levels, **OR** recruit to the next cohort.

Note: Depending on the outcome of the TSG review where patients have experienced a Grade 2 MOv18 related AE, it may be deemed appropriate to move to the next dose level. Assessment for this will be made on a case by case basis. Grade ≥ 2 rash will generally not preclude intra-patient dose escalation or opening of the next cohort.

If a DLT is experienced in Cycle 1 or Cycle 2, treatment will be withheld until toxicity resolves to baseline or Grade 1. Upon resolution, if appropriate, MOv18 IgE may be recommenced at a lower dose, or the patient may withdraw from study treatment. The cohort will be expanded, and a decision will be made by the TSG whether to expand the cohort by 1 or 2 patients, depending on the nature of the DLT observed (e.g. its nature, grade, expectedness and clinical significance).

Table 3: Planned intra-patient dose escalation scheme

Cohort	Cycle 1 Dose level	Cycle 2 Dose level	No. planned patients/cohort
7 ⁽ⁱ⁾	6 mg	*12mg	1**
8 ⁽ⁱ⁾	12 mg	*20mg	1
9 ⁽ⁱ⁾	20mg	*40mg	1

[figure not shown]
* If required, intermediate dose levels may be explored for the starting dose in Cycle 2, this will be discussed at the dose review meeting and is dependent on the emerging safety profile.

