(g) **Vital signs (BP, pulse rate and temperature)** should be performed for each infusion of MOv18 IgE within the 30 min (± 5 min) pre-dose, every 15 min (± 5 min) during the first and second infusions, 15 min (± 5 min) and 30 min (± 5 min) after completion of each infusion, and before discharge from the clinic. For the first infusion only, vital signs are additionally required (± 10 min) at 1h, 2h, 4h, 8h, 12h, 18h and 24h after completion of the infusion, and as clinically indicated. Monitoring with a pulse oximeter is required continuously throughout each infusion until 30 min after completion of the infusion. For intra-patient dose escalation cohorts, these assessments are to also be performed on Cycle 2 Day 1.

(h) 1 mL blood sample for 200 μ L serum for measurement of **serum tryptase** at baseline and on completion of every infusion of MOv18 IgE. Additional samples may be taken in response to a positive skin prick test or in patients who experience a suspected anaphylactic reaction, such as urticaria or severe or infusion-related symptoms necessitating interruption or discontinuation of the infusion (see protocol section 7.2.1 and 7.2.5 for details of when to take these samples). Samples will be analysed and reported prior to next dose for 2nd and 3rd doses. Subsequent samples can be analysed on request of the Investigator in response to clinical symptoms and reported prior to next dose.

(i) 3.5 mL blood sample for 1-2 mL serum for **PK assessment of circulating MOv18 IgE** at 7 time points: Pre-dose on Cycle 1 Day 1 (within 24 h of infusion), 30 min (± 5 min)*, 2 h (± 30 min), 4 h (± 30 min), 6 h (± 30 min), 24 h (± 2 h), and possibly* at 48 h (± 2 h) post-dose; Cycle 1 Day 8 Pre-dose; (total blood volume ~ 25 mL). If a time point has been missed, a sample should be taken as soon as possible and the time recorded. *The 30 min (± 5 min) sample may be replaced by the 48h (± 2 h) post-dose sample at higher dose cohort levels (refer to the study laboratory manual for which sample to take). Additional samples should be taken at 0, 2 and 6 hours following a suspected anaphylactic/urticarial reaction or positive skin prick test (see protocol section 7.2.1 and 7.2.5 for details).

(j)

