(k) 6 mL blood sample for **basophil activation test (BAT)** at Day -7 to Pre dose Cycle 1 Day 1 and 2 h (± 30 min) after the end of infusion of MOv18 IgE at the first and third infusions (Cycle 1 Day 1 and Cycle 1 Day 15) (total blood volume 18 mL). Additional samples should be taken immediately (0 hours) following a suspected anaphylactic reaction, urticarial, or severe infusion-related symptoms necessitating interruption or discontinuation of the infusion or positive skin prick test (see protocol section 7.2.1 and 7.2.5 for details). For intra-patient dose escalation cohorts, a sample will also be taken on Cycle 2 Day 1, 2 h (± 30 min) after the end of infusion of the higher dose of MOv18 IgE.

- (l) [REDACTED]
- (m) [REDACTED]
- (n) [REDACTED]
- (o) [REDACTED]
- (p) Monthly **follow-up** required ONLY for those AEs and SAEs considered drug-related (highly probable, probable or possible) and present at the Second Post-treatment Safety Assessment. Monthly follow-up to continue until resolution, return to baseline, stabilisation or patient starts another anti-cancer treatment.
- (q) All patients, who are removed from the study for reasons other than progressive disease, must be re-evaluated at the time of treatment discontinuation, unless a **tumour assessment** was performed within the previous four weeks.
- (r) For patients unable to attend in person for the **Second Post-treatment Safety Assessment** due to concurrent illness, progressive disease or other reasons, the safety assessment may be made by telephone and the sample for PK assessment omitted.
- (s) ECG to be performed after completion of the infusion.
- (t) For intra-patient dose escalation cohorts, these assessments are to also be performed on Cycle 2 Day 1.
- (u) For intra-patient dose escalation cohorts, the post dose biopsy should be performed following at least the first dose in Cycle 2 where possible.

Table 5: Schedule for Maintenance Dosing Period

Observation/Investigation	Screening/ Baseline	Initial Dosing Period	Maintenance Dosing Period (MOv18 IgE dosing every 14 ± 2 days)			First Post- treatment Safety Assessment	First Post- treatment Safety Assessment		
			7th dose	8th dose	9th dose	28 days ± 7 days after final dose	70 days +/- 14 days after final dose		
Adverse event evaluation			Continually review			As in Table 4	As in Table 4		
Concomitant treatments			Continually review						
Radiological disease assessment	As in Table 4	As in Table 4	Every 6 weeks						

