16.5 Appendix 5: Trial-specific Grading of IgE-associated Mast Cell Degranulation (anaphylaxis)

Grade 1	Grade 2	Grade 3	Grade 4	Grade 5
No infusion-related symptoms or mild symptoms not requiring treatment, in the presence of a positive serum tryptase assay	Therapy or infusion interruption indicated but responds promptly to symptomatic treatment (e.g. antihistamines, NSAIDS, IV fluids), in the presence of a positive serum tryptase assay	Prolonged and/or severe symptoms with hypotension (systolic BP < 100 mmHg) and/or angioedema, laryngeal oedema, bronchospasm or hypoxia* (sats <92% on room air), in the presence of a positive serum tryptase assay	Life-threatening consequences (pressor or ventilatory support indicated), in the presence of a positive serum tryptase assay	Death

** - for patients with lung metastases whose baseline saturations on air may be significantly lower than 100%, hypoxia is defined as a drop in saturations requiring the administration of oxygen*

In general, rapid onset of urticaria suggests mast cell degranulation (anaphylaxis) rather than cytokine release syndrome. However, urticaria alone appears to be a common but manageable symptom of MOv18 IgE infusion.

Note: for this study, a positive serum tryptase assay is required for infusion-related events to be ascribed to IgE-associated mast cell degranulation (anaphylaxis).

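### Table 4 footnote (h) does not commit to reading tryptase at doses 4 to 6, so a symptom-free Grade 1 anaphylaxis in Cycle 2 could be absent from the dose review that follows

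*Protocol*

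**What the plan says.** **Collection.** Section 5.3.1 and Table 4 require a tryptase sample at the end of every infusion, which gives six post-infusion samples in the Initial Treatment Period.

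**Analysis.** Footnote (h) of Table 4 makes one firm commitment: "Samples will be analysed and reported prior to next dose for 2nd and 3rd doses". For later samples it says: "Subsequent samples can be analysed on request of the Investigator in response to clinical symptoms and reported prior to next dose".

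**Role of the result.** Appendix 5 requires a positive tryptase before an event is called anaphylaxis. Its Grade 1 reads: "No infusion-related symptoms or mild symptoms not requiring treatment, in the presence of a positive serum tryptase assay". Section 5.3.1 adds that "grading of these events will be performed only in retrospect when results of serum tryptase assays are available".

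**Weight of the event.** Sections 3.1 and 3.3.2 make any Appendix 5 event a dose-independent significant toxicity, listed under the primary objective with no lower limit on grade. Section 9.2.2 makes every grade an SAE. Section 3.4.2 asks the Trial Steering Group (TSG) to weigh Grade 1 events.

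**Decision points for escalated patients.** Section 5.4 bases escalation mainly on the first two doses in a cohort, "or the first two doses of cycle 2 for patients undergoing intra-patient dose escalation". Section 5.4.1 then provides: "An additional dose review meeting will be held following completion of Cycle 2 prior to confirming the opening of the next cohort".

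**The concern.** The trigger for reading a later sample is a clinical symptom, but one form of the event has none. A symptom-free Grade 1 event at dose 4, 5 or 6 would sit in collected serum that no visible sentence requires anyone to assay.

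In flat-dose cohorts the committed readings roughly match the doses that drive the decision. For escalated patients the decision doses become 4 and 5, and footnote (h) commits to neither. At stake is the completeness of a primary safety endpoint, of SAE reporting, and of what the TSG sees when it decides whether the next cohort opens.

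The protocol regards anaphylaxis as unlikely to be dose-related, but later infusions still carry information. Section 3.3 says of a mast-cell reaction: "Such a reaction would be predicted to persist and probably worsen with subsequent infusions".

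**Working it through.** **1. Committed tryptase readings.** Footnote (h) can be read in two ways: as samples reported before doses 2 and 3 (drawn at infusions 1 and 2), or as samples drawn at infusions 2 and 3.

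| Count | Reported before doses 2, 3 | Drawn at doses 2, 3 |
|---|---|---|
| All six post-infusion samples | 2 of 6 | 2 of 6 |
| Flat-dose decision doses (1, 2) | 2 of 2 | 1 of 2 |
| Escalated decision doses (4, 5) | 0 of 2 | 0 of 2 |
| All Cycle 2 samples (4, 5, 6) | 0 of 3 | 0 of 3 |

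The Cycle 2 result is the same either way.

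**2. Could the footnote mean the 2nd and 3rd doses of each cycle?** Table 4's column heading refers to each three-week cycle, so the question is fair. But footnote (k) equates the first and third infusions with Cycle 1 Day 1 and Cycle 1 Day 15, and Table 5 numbers doses 7 to 9 across the whole course. Dose numbers therefore run through the course. If a per-cycle meaning was intended, footnote (h) needs to say so.

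**3. Which planned doses never get a committed reading?** From Table 3:

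| Cohort | Cycle 1 (committed readings) | Cycle 2 (none) |
|---|---|---|
| 7(i) | 6 mg | 12 mg |
| 8(i) | 12 mg | 20 mg |
| 9(i) | 20 mg | 40 mg |

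The doses 12 and 20 mg are first given without a committed reading, then receive one in the next cohort's Cycle 1, in a different patient. Only 40 mg never does: three samples in the one planned patient. Across all three planned patients, if all escalate and complete, 3 x 3 = 9 Cycle 2 samples have no committed reading.

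**4. Do other safeguards find a silent Grade 1 event?** Section 7.2.1 requires a skin prick test before every infusion, and for the basophil activation test footnote (k) says: "For intra-patient dose escalation cohorts, a sample will also be taken on Cycle 2 Day 1". Neither replaces tryptase under Appendix 5. The extra tryptase samples in Section 7.2.5 need urticaria or another clinical sign. Section 8 allows the frequency of analysis to be reconsidered, and a note to Table 6 allows some assays in batches before study end. Neither provision is tied to the post-Cycle 2 review.

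**5. Minor related point: pharmacokinetics.** The plan's own volume reproduces: 7 samples x 3.5 mL = 24.5 mL (Section 8.2). Cycle 2 Day 1 repeats only the Day 1 series, 6 x 3.5 = 21.0 mL, so the last sample is at 24 h, or at 48 h if that replaces the 30-minute one. With half-life T of 1 to 2 days (Section 2.2.5), mono-exponential decline (assumed) and a 1.5 h infusion, the share of AUC to infinity that is extrapolated beyond a last sample t hours after the infusion is

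(1 - exp(-1.5k)) / (1.5k) x exp(-kt), with k = ln 2 / T.

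| Last sample | T = 24 h | T = 48 h |
|---|---|---|
| 24 h | 48.9% | 70.0% |
| 48 h | 24.5% | 49.5% |
| Day 8 pre-dose (t = 166.5 h) | 0.8% | 8.9% |

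**The case against.** The case for leaving the text alone has real substance, and much of it limits the finding.

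- **No explicit rule is affected.** A reader might infer that a stopping or escalation boundary runs blind in Cycle 2. It does not. Recruitment suspension and the frequency assessment concern anaphylaxis above Grade 1. The rules in Section 5.4.1 turn on related events of Grade 2 or higher, or on DLT. Appendix 5 Grade 2 involves treatment or interruption of the infusion, so it is clinically apparent. This stands.
- **The next cohort re-tests the dose.** A reader might infer that 12, 20 and 40 mg all go permanently unread. On the planned path that is true only of 40 mg. This stands, although the re-test is in another patient and comes after the review in question.
- **Footnote (h) was not uniquely overlooked.** Footnotes (g), (k) and (t) do reach Cycle 2 Day 1, which might suggest that (h) was left behind. Those footnotes extend assessments and sample collection. Tryptase collection needed no extension, and no visible text fixes when the activation test or PK samples are assayed for a dose review either. This stands.
- **The later samples may be read anyway.** Footnote (h) could be only a rule on fast reporting. Section 7.2.5 sorts infusion-related events by tryptase result, which presupposes results. Table 6 is redacted and the laboratory manual is not shown. This is possible, so the documents do not support saying that these samples will never be analysed. They support only that no visible commitment exists before the review.
- **Silent reactions should declare themselves.** If reactions worsen with repeated exposure, later symptoms would prompt testing. This stands only in part: a first rise at dose 6 has no later Cycle 2 infusion to reveal it before the review.

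**Conclusion.** The point holds in a narrow form. As the visible text stands, 0 of 3 Cycle 2 tryptase samples per escalated patient have a committed reading, and the fallback trigger cannot detect a Grade 1 event without symptoms. Such an event belongs to the primary endpoint, must be reported as an SAE and is to be considered by the TSG, yet it could be absent when the post-Cycle 2 review takes place.

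The loss is one of ascertainment and of information for TSG judgement, not of a numerical safeguard. The documents give no rate for silent tryptase rises, and the 1% and 20% figures in Section 3.4.2 concern events above Grade 1, so no probability is attached here. The conclusion assumes that the planned Table 3 path is followed and that neither Table 6 nor the laboratory manual already requires the readings.

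The PK point is minor. Terminal half-life and AUC to infinity at 40 mg would be poorly supported, but the stated endpoint is serum concentrations, Cmax and Tmax are unaffected, a 48 h sample is possible and Section 8 allows sampling to be revised.

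**What to change.** Amend Table 4 footnote (h) so that, for intra-patient escalation cohorts, the tryptase samples already collected at doses 4 to 6 are analysed routinely, with all results available for the post-Cycle 2 dose review. If Table 6 or the laboratory manual already provides for this, a cross-reference in footnote (h) is enough. The cost is about three assays per escalated patient, or nine if all three planned patients escalate and complete, on existing serum and with no extra visit. No dose or clinical rule changes.

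Optionally, add one 3.5 mL pre-dose PK sample on Cycle 2 Day 8 for escalated patients in Table 4, Section 8.2 and Table 7. It can be taken at the existing pre-dose draw and brings the Cycle 2 PK volume from 21.0 to 24.5 mL, equal to Cycle 1.
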